### 1.8. TREATMENT OPTIONS

The range of available treatment options for NMSC includes surgery, cryotherapy, curettage and electrodesiccation, radiation therapy including superficial radiation therapy, photodynamic therapy, various forms of brachytherapy, and chemotherapeutic agents. Treatment decisions may be based on tumor type, anatomical location, patient age, tumor stage and classification, physician preference, and treatment setting. The choice of treatment becomes more complex among the elderly due to frailty, limited life-expectancy, and comorbidities. Anatomical location also becomes an important factor as NMSC lesions commonly occur on the ears, eyes and nose where treatment may have significant cosmetic consequences.

This study will focus on evaluation of outcomes of Superficial X-ray Therapy (SRT), a non-surgical option for patients with primary non-aggressive BCC and SCC and for patients who decline surgery or are poor surgical candidates.

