### 3. SUPPORTIVE LITERATURE

The following study published in 2012 is similar in design and purpose to the current retrospective trial.

Superficial x-ray in the treatment of basal and squamous cell carcinomas: A viable option in select patients

J Am Acad Dermatol December 2012 Volume 67, Issue 6, Pages 1235–1241

[name], Brett M. Howard, BA, Henry P. Heaton, BA, [name], Hyokyong [name], and W. [name]

The abstract from this publication is presented below.

*Background:* Effective nonsurgical modalities are limited in the treatment of basal cell carcinoma (BCC) and squamous cell carcinoma (SCC).

*Objective:* We sought to evaluate the efficacy and viability of superficial x-ray therapy in the treatment of BCC and SCC in an outpatient setting.

*Methods:* A retrospective analysis was performed on 1715 histologically confirmed primary cutaneous BCC and SCC treated with superficial x-ray therapy at Dermatology Associates of Tallahassee in Florida between 2000 and 2010.

*Results:* Of the 1715 tumors reviewed during this period, 712 were histologically proven BCC (631 nodular and 81 superficial), 994 were SCC (861 SCC in situ and 133 invasive SCC), and 9 displayed distinct features of both BCC and SCC in the same biopsy specimen. Kaplan-Meier estimates (with 95% confidence intervals) of cumulative recurrence rates of all tumors at 2 and 5 years were 1.9% (1%-2.7%) and 5.0% (3.2%-6.7%), respectively; of BCC at 2 and 5 years were 2% (0.8%-3.3%) and 4.2% (1.9%-6.4%),

respectively; and of all SCC at 2 and 5 years were 1.8% (0.8%-2.8%) and 5.8% (2.9%-8.7%), respectively. Tumors on male patients and those with a diameter greater than 2 cm were associated with a statistically significant increase in recurrence likelihood.

*Limitations:* This study represents only patients treated in 1 dermatology office in North Florida and may not be representative of the general patient population.

*Conclusions:* Superficial x-ray therapy remains a viable nonsurgical option for the treatment of primary BCC and SCC in patients where surgical intervention is declined, inadvisable, or potentially associated with significant cosmetic or functional limitations.

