The present study's design and intent is to confirm and expand upon these findings. In particular, the limitation of the prior study of homogeneity of the population source from which the data was drawn will be overcome in the present study, as data from numerous sources will be collated and evaluated collectively such that the findings will be representative and generalizable to the general patient population.

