### **5.4.1. Inclusion Criteria**

1. Male or female.
2. Treatment with SRT-100™.
3. Treatment date of December 31, 2015 or earlier.
4. Non-Melanoma Skin Cancer (NMSC) pathological diagnosis of confirmed squamous cell carcinoma (SCC) or basal cell carcinoma (BCC).

5. Histopathological Grade: G1 (well differentiated); G2 (moderately differentiated) or Gx (not assessed).
6. One lesion is treated, or more than one lesion is treated with a minimum of a 5 mm gap between the edges of the lesion margins.
7. Required retrospective data is existing and sufficient.

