#### **5.4.2. Exclusion Criteria**

1. Lesions of etiology other than non-melanoma skin cancer (NMSC).

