#### **A. Patient Information and Demographics:**

1. Gender
2. Age at treatment start

3. Ethnicity
4. Significant comorbidities

B. Lesion Diagnostic Variables and Characteristics:

1. Pathology diagnosis
2. Diagnosis subtype/variant
3. Other pathology
4. Recurrent lesion (yes/no)
5. Previous treatment if recurrent
6. Lesion location (no restrictions): scalp, mastoid, forehead, cheek, nose, ear, chin, lips, neck, upper arm, lower arm, hand, upper leg, lower leg, foot.

C. Lesion Size and Margins:

1. Lesion size
2. Treatment margin
3. Lead cutout size
4. Applicator size

D. Treatment Dosage and Schedule:

1. Treatment dose
2. Number of treatments
3. Number of treatments per week
4. Treatment span(days)

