#### **10.1.2. Recurrences and Complications**

Each identified incidence of lesion recurrence, complication or adverse event recorded at any point throughout the treatment and follow-up evaluation phase will be explored descriptively. Statistical evaluation of recurrences will be as follows:

- (i) *Kaplan-Meier Survival Probability Estimates* will be calculated across the duration of available follow-up data, reporting survival probability estimates, and lower and upper limits of the 95% Confidence Interval by follow-up year.
- (ii) *Log-Rank Test* will be performed to evaluate for differences in recurrence-free survival between lesion types.
- (iii) *Multivariate Cox Regression Analysis* will be performed to account for the contribution of the potential influential factors of gender, age, lesion type, lesion size, total treatment dosage and TDF to recurrence-free survival.

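### Lesions already recurrent at entry are admitted and flagged, but no planned analysis separates or adjusts for them, and no primary-lesion estimate is planned

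*Combined protocol and SAP*

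**What the plan says.** **Who enters.** Section 5.4.1 requires a "pathological diagnosis of confirmed squamous cell carcinoma (SCC) or basal cell carcinoma (BCC") and treatment with the device. It does not ask that the lesion be primary. The only exclusion in 5.4.2 is "Lesions of etiology other than non-melanoma skin cancer (NMSC"). A lesion that recurred after earlier treatment therefore qualifies.

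**What is recorded.** Section 6.3 B lists "Recurrent lesion (yes/no") as item 4 and "Previous treatment if recurrent" as item 5, so the protocol expects such lesions. Item B.4 is status at entry. It differs from 6.3 F.2, recurrence after SRT, which is the outcome.

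**What is analysed.** Section 10.1.1 gives one cure percentage over all lesions. Section 10.1.2(i) gives Kaplan-Meier estimates by follow-up year with no stratum named. The log-rank test in (ii) compares lesion types, which 10.2.2 identifies as BCC and SCC. The Cox model in (iii) covers the "potential influential factors of gender, age, lesion type, lesion size, total treatment dosage and TDF to recurrence-free survival". The analyses in 10.2 are overall or by BCC/SCC, and none tabulates recurrent status.

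**What it is set against.** Section 3 presents a series of "1715 histologically confirmed primary cutaneous BCC and SCC" and adds: "The present study's design and intent is to confirm and expand upon these findings". Section 1.8 describes SRT as "a non-surgical option for patients with primary non-aggressive BCC and SCC", and also as an option for people who refuse surgery or are unsuited to it.

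**The concern.** A lesion that has come back after treatment may carry a different risk from an untreated one. Section 1.6 itself makes recurrence and evidence of earlier treatment part of the clinical assessment. If the risks differ, two things follow.

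First, the overall cure rate and Kaplan-Meier curve depend on how many recurrent lesions the sites contribute. They would not estimate the same quantity as the primary-tumour series that the study sets out to confirm.

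Second, relating outcome to dose and fractionation is a stated secondary objective. If recurrent lesions were dosed differently, the dose and TDF coefficients would carry part of the effect of recurrent status, and the model as listed could neither show nor remove it.

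**Working it through.** The plan states no sample size, event count or expected rate for this registry, so there is no planned figure to reproduce. The omission is established by the text above. The arithmetic below only shows what it could amount to.

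**Inputs**
- p = 5.0%: five-year cumulative recurrence, all tumours, cited series in section 3 (95% limits 3.2% to 6.7%). Its tumour counts are consistent: 712 + 994 + 9 = 1715.
- w: share of recurrent lesions. Not in the documents; assumed 10%, 20% and 30%.
- HR: hazard ratio, recurrent versus primary. Not in the documents; assumed 1 to 3, where 1 means no difference.

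**Step 1: pooled five-year recurrence**

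Risk in recurrent lesions = 1 − (1 − p)^HR. At HR 2 this is 1 − 0.95² = 9.75%.

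Pooled risk = (1 − w) × p + w × [1 − (1 − p)^HR]. At HR 2 and w = 10% this is 0.9 × 5.0% + 0.1 × 9.75% = 5.48%.

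| Assumed HR | Risk, recurrent lesions | Pooled, w = 10% | Pooled, w = 20% | Pooled, w = 30% |
|---|---|---|---|---|
| 1 | 5.00% | 5.00% | 5.00% | 5.00% |
| 1.5 | 7.41% | 5.24% | 5.48% | 5.72% |
| 2 | 9.75% | 5.48% | 5.95% | 6.42% |
| 3 | 14.26% | 5.93% | 6.85% | 7.78% |

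Up to HR 2, every value stays below the cited upper limit of 6.7%. At HR 3 the pooled value passes it once the share reaches 20%.

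**Step 2: apparent dose effect when there is none**

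Take two dose groups with the same true hazards but different recurrent shares. The apparent dose HR is the ratio of five-year cumulative hazards, −ln(1 − pooled risk). At HR 2 with shares of 10% and 40%, the pooled risks are 5.475% and 0.6 × 5.0% + 0.4 × 9.75% = 6.90%. The ratio is ln(0.9310) / ln(0.94525) = 1.27.

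| Assumed HR | 10% versus 20% recurrent | 10% versus 40% recurrent |
|---|---|---|
| 1.5 | 1.05 | 1.14 |
| 2 | 1.09 | 1.27 |
| 3 | 1.16 | 1.49 |

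These are unadjusted ratios. The planned covariates (gender, age, lesion type and size) might absorb some of the effect. If dosing does not differ by recurrent status, the shares are equal and the ratio is 1.

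**The case against.** **A wider population is legitimate.** The stated intent is to expand on the cited series as well as confirm it. Section 1.8 is background, and its second group is not limited to primary lesions. Section 10 plans no formal comparison with the series. All of this stands. A reader might infer that admitting recurrent lesions is an error or contradicts the protocol; the documents do not support that. What remains is narrower: the confirming part of the aim needs a primary-lesion estimate, and none is planned.

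**The size is assumed.** This also stands. Nothing in the documents shows that recurrent lesions do worse, how many there are, or that they were dosed differently. One might conclude that the pooled rate is biased, or that the dose objective fails, but neither can be claimed. Many of the scenarios above would not visibly depart from the cited interval.

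**The objectives are worded openly.** Section 5.1.2 gives lesion variables only as examples, so recurrent status could be examined under it. That does not fill the gap, because the Cox list in 10.1.2(iii) names its six factors and leaves this one out.

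**Double counting.** A reader might infer that a lesion that failed SRT-100 and was re-treated will be entered twice, once as a recurrence and once as a cure. The documents do not say so. They do not state that any previous treatment was SRT-100, and 6.3 F.3 already gives later treatment and its outcome a place on the original record. It is only a possibility, because no text bars a second record.

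**Conclusion.** The point holds as an omission in the analysis plan. A baseline field that the protocol thinks worth collecting is not tabulated, stratified on or adjusted for. Followed as written, section 10 yields outcome estimates mixed over an unknown share of recurrent lesions and dose terms unadjusted for recurrent status.

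Confidence is high on the omission and low on its effect. With a recurrent share of 10% to 30%, the shift from 5.0% runs from nothing at HR 1 to 2.8 percentage points at HR 3 (7.78% − 5.00%). The dose distortion is a further conditional: it needs both a different prognosis and different dosing. Only a result split by recurrent status can show whether either matters, so the change should be made, although nothing here shows that the pooled results will mislead.

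**What to change.** 1. In 10.1.1 and 10.1.2(i), report cure rate and Kaplan-Meier estimates for primary and recurrent lesions separately, as well as overall. State that any comparison with the cited series uses the primary-lesion result.
2. In 10.1.2(iii), add recurrent status at entry (6.3 B.4, not the outcome F.2) to the Cox covariates.
3. In 10.2.2, tabulate recurrent status.
4. As a secondary precaution, instruct sites that a later SRT-100 course to the same lesion is recorded only under 6.3 F.3.

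**Cost.** Items 1 to 3 need no new data. They add one Cox term and a recurrent stratum that may be small, with wide limits. The term is there for adjustment, not as a test. At an assumed 80% power and two-sided 5% level, detecting HR 2 with a 10% share would take about (1.96 + 0.84)² / (0.1 × 0.9 × (ln 2)²) ≈ 182 recurrences.

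Item 4 needs a little more care. Codes are assigned per subject (7.2.1), and 6.3 lists neither a lesion identifier nor a treatment date, so the rule could not be checked in the database. Sites would have to apply it from the charts at extraction, before the link sheets are destroyed under 7.2.1.

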### Setting/Participants

- Retrospective data will be collected from medical records of patients treated for NMSC with the SRT-100™ prior to January 1, 2015, with follow-up data available.
- There will be multiple participating study sites in the United States who have access to the required patient population medical records.
- The number of participants will be determined by the number of qualifying patient files identified cross all participating sites.
- Medical record retrospective data will be included for males and females treated with SRT-100™ prior to January 1, 2015

- January 1, 2015 and for whom follow-up data is available. Subjects will have NMSC pathological diagnosis of confirmed squamous cell carcinoma (SCC) or basal cell carcinoma (BCC) with Histopathological Grade of G1 (well differentiated); G2 (moderately differentiated) or Gx (not assessed in report), Qualifying subjects had a single lesion treated, or more than one lesion treated with a minimum 5 mm gap between the edges of the lesion margins.

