## 2 STUDY JUSTIFICATION AND RATIONALE

Non-melanoma skin cancers are the most common form of cancers with the incidence increasing at a rapid rate. Current guidelines (e.g. National Comprehensive Cancer Network (NCCN) and American Academy of Dermatology (AAD)) suggest that surgical treatments remain the most effective option for the management of most cases of BCC and SCC.

Clinical recommendations for radiation therapy (RT) are typically based on consideration of RT as a single category without differentiating between the different applications of the different available modalities. As different radiotherapy modalities and dosing have been shown to result in widely varying outcomes, with recurrence rates ranging from 2.8% to 30%, such generalized recommendations can be misleading. AAD guidelines group newer technologies such as high-dose electronic brachytherapy (EBT) and SRT as new therapies. Though the AAD has since clarified these modalities in an addendum position statement it continues to refer to SRT as a “new” technology that “differs substantially from traditional external beam radiation therapy” and one in need of “research on long term outcomes.”

This retrospective study has been designed to focus on efficacy and safety of superficial radiation therapy (SRT) for NMSC and to specifically address this AAD-highlighted deficiency and need for long-term evaluation of ‘new’ technologies for the treatment of NMSC. Evaluation of SRT for NMSC in this study will be via review of retrospective data for procedures delivered by the Sensus Healthcare SRT-100™. Sensus Healthcare’s SRT-100™ has been cleared by the U.S. Food and Drug Administration (U.S. FDA) for the treatment of non-melanoma skin cancer and keloids.

The SRT-100™ delivers a precise, calibrated dose of superficial radiation therapy that only penetrates skin deep, resulting in a virtually painless treatment can be safely administered in the physician’s office.

Low-dose SRT effectively destroys BCC and SCC without any invasive cutting, bleeding or stitching. There is no need for anesthesia, no risk of infection or scarring and no need for reconstructive plastic surgery. Healing time is quick with minimal to no post-treatment downtime or lifestyle restrictions. It is therefore both a viable and highly desirable alternative to invasive, painful and higher-risk surgical procedures.

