### **5.3.2. Total Number of Study Sites/Total Number of Subjects Projected**

There will be multiple participating study sites, all located in the United States. Each will be selected based upon having access to the required medical records of patients who were treated at their site for NMSC with the SRT-100™ prior to January 1, 2015, and for whom follow-up data is available. There is no limit on the potential number of participating sites. Each identified and qualifying site that is willing and able to participate in the study will be included.

Subject data will be retrospectively collected from the existing medical records in the identified qualifying patient files at the participating sites as those who were treated with the SRT-100™ for one or more NMSCs, who have follow-up data and who subsequently satisfy all of the inclusion criteria and none of the exclusion criteria for inclusion of their retrospective data in this study. There is no limit on the potential number of study subjects. The applicable retrospective data for each identified and qualifying subject at each participating study site will be included in the retrospective analysis.

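### The six-factor Cox model has no safeguard for sparse recurrences: with fewer than about 20 to 25 events the default fit can give infinite or extreme hazard ratios

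*Combined protocol and SAP*

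**What the plan says.** Section 10.1.2(iii) commits to a single multivariate Cox model relating the "potential influential factors of gender, age, lesion type, lesion size, total treatment dosage and TDF to recurrence-free survival". It does not state the estimation method, the covariate coding, a minimum number of recurrences, a reduced model, or what happens if the fit does not converge.

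No size is planned. The abstract (Setting/Participants) says: "The number of participants will be determined by the number of qualifying patient files identified cross all participating sites". Section 5.3.2 adds: "There is no limit on the potential number of study subjects". There is thus no cap, but also no floor. Section 5.3.1 follows each patient to the latest chart entry and sets no minimum follow-up.

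Section 3 gives the benchmark that the study aims to confirm and extend. In that earlier series, "A retrospective analysis was performed on 1715 histologically confirmed primary cutaneous BCC and SCC" treated at one practice, and the cumulative recurrence rates "of all tumors at 2 and 5 years were 1.9% (1%-2.7%) and 5.0% (3.2%-6.7%), respectively". Section 2 also cites recurrence between 2.8% and 30% across radiotherapy modalities and dosing.

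**The concern.** A Cox model draws its information from events, not from lesions. If recurrences are few, a covariate pattern can by chance contain none of them, or all of them. The ordinary maximum partial-likelihood estimate for that factor is then infinite, or very large with a useless standard error.

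This model carries much of the secondary objective. The log-rank test in 10.1.2(ii) compares lesion types only. Section 10.2 consists of descriptive summaries and t-tests comparing BCC with SCC on size, follow-up and treatment variables, and none of these has recurrence as its outcome. For gender, age, lesion size and dose, the Cox model is the only planned link to recurrence. An unstable fit would either fail, leaving the analyst to improvise after seeing the data, or put erratic hazard ratios into the intended publication.

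**Working it through.** The plan states no sample size, event count or power, so there is no figure of its own to reproduce.

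**1. Recurrences implied by the comparator series.** Inputs are the Kaplan-Meier rates and 95% limits in Section 3. Formulas: SE = (interval width)/3.92; H = −ln(1 − rate); Var(H) = (SE/(1 − rate))². Within a time interval, effective number at risk n = ΔH/ΔVar, and events = ΔH × n.

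- Years 0–2: SE = 0.017/3.92 = 0.00434; H = 0.01918; Var = 1.954 × 10⁻⁵; n ≈ 982; events ≈ 18.8.
- By year 5: SE = 0.035/3.92 = 0.00893; H = 0.05129. For years 2–5, ΔH = 0.03211; ΔVar = 6.879 × 10⁻⁵; n ≈ 467; events ≈ 15.0.
- Total ≈ 33.8. Moving every published figure by ±0.05 percentage points gives about 30 to 38.
- Per covariate: 33.8/6 = 5.6. Yield per lesion: 33.8/1,715 = 2.0%.

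Multiplying 1,715 by 5.0% would give 86 events, but only if every lesion had five complete years of follow-up.

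**2. Lesions needed for 25 recurrences.** The yield in this registry is unknown, so a range is shown.

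- Comparator's yield to year 5: 25 × 1,715/33.8 ≈ 1,270 lesions.
- 5% five-year recurrence with follow-up uniform from 0.2 to 6 years, as simulated below (about 19 events per 600 lesions): 25 × 600/19 ≈ 790.
- 5% recurrence, all followed for five years: 25/0.05 = 500.
- 30% recurrence (top of the Section 2 range), complete follow-up: 25/0.30 ≈ 83.

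A registry of 600 lesions would therefore have about 12 recurrences at the comparator's yield (33.8 × 600/1,715), about 19 under the simulated follow-up, and 30 with complete follow-up.

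**3. Behaviour of the ordinary fit.** These results are simulated. Apart from the 58% SCC share and the recurrence rates, the assumptions are not in the documents: 60% male, 10% large lesions, dose–TDF correlation 0.8, and hazard ratios of 2.0 (male), 1.3 (age, per SD), 1.3 (SCC), 3.0 (large), and 0.8 each (dose and TDF, per SD). With all lesions followed for five years, the ordinary fit gave:

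| Events (mean) | Non-finite fits | 90th percentile of male HR (true 2.0) |
|---|---|---|
| about 10 | 18% | 5.0–5.2 |
| 14–15 | 5–8% | 4.9–5.8 |
| 24 | 0.2% | 4.1 |
| 32 | 0.3% | 3.5 |
| 49 | 0% | 3.1 |
| 148 | 0% | 2.6 |

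The percentiles are among finite fits. The failure rate depends on the assumptions. With follow-up uniform from 0.2 to 6 years and 300 lesions, it was 7% with independent covariates (median 10 events) and 24% with the correlated set above (median 9 events, counting any |log HR| above 5 as extreme). At 600 lesions (19 events) it was 1.3%.

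**4. Ordinary against Firth.**

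- About 10 events: 18% of ordinary fits had an extreme coefficient, against 0% with Firth.
- 19 events: 1% against 0%. Among finite fits, RMSE of the male log HR was 0.61 ordinary and 0.54 Firth.
- 31 events: 0.40 and 0.37.
- 52 events: 0.34 and 0.32.

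Firth's error was no higher at any size tested.

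**The case against.** **The estimator is not stated.** Firth's method is itself a way to fit a Cox model, so the plan does not choose the wrong estimator; it is silent. That stands. Ordinary partial likelihood is only what an analyst would use by default.

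**The registry may be large enough.** It is multi-site and uncapped, and one practice alone implies about 34 recurrences by year 5. If the registry merely matches that practice, the change does almost nothing. Treatment ended by 2014 or 2015 and the references run to 2018, so potential follow-up is at least about two years. Recurrences after year 5 also count, and recurrent lesions are not excluded. All of this could raise the yield, although how complete the charts are is unknown. This limits the concern to a registry with few events, but the plan contains nothing that rules such a registry out.

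**Inflation.** A reader might infer that hazard ratios will be systematically exaggerated unless the registry is very large. The check does not support that. Median male hazard ratios were 2.16 and 2.02 for a true 2.0. Mean log hazard ratios among finite fits were mostly within about 15% of truth, though up to 26–28% too large for some coefficients at 1.6 to 2.3 events per covariate. Coverage of ordinary 95% intervals was about 92% to 98%. Averages taken over all fits look worse only because diverged fits dominate them.

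**Imprecision remains.** Firth does not create information. With 300 lesions and about 10 events (independent covariates), 33% of its male hazard ratios were still wrong by more than two-fold, against 40% with the ordinary fit. That stands, and it is why the event count should be printed.

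**Conclusion.** The concern holds as a missing safeguard. The plan fits six covariates whatever the number of recurrences, has no event floor, and takes as its benchmark a series with only about 34 recurrences (30 to 38) in 1,715 lesions. Below about 20 to 25 recurrences the default fit is unreliable: roughly 7% to 24% of fits are non-finite or extreme at about 10 events, about 1% at 19, and almost none above 25 to 30. With about 35 or more events the choice of estimator matters little.

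These thresholds rest on simulated covariate distributions and follow-up that the documents do not give. A fixed rule on events per covariate is a rule of thumb and is not relied on here. The 30% in Section 2 spans modalities and dosing; the superficial x-ray series in Section 3 is the closer guide, but neither settles this registry's yield. The change is worth making because it must be specified before the event count is known and loses nothing if events prove plentiful.

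**What to change.** In Section 10.1.2(iii), state that the Cox model will be fitted by Firth's penalised partial likelihood, with penalised profile-likelihood 95% confidence intervals. Report the number of recurrences, and recurrences per covariate, beside the table of hazard ratios.

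The profile intervals treat lesions as independent, as ordinary Cox intervals do. Inclusion criterion 6 admits patients with more than one lesion, so add that intervals will come from a bootstrap resampling patients if patients contribute several lesions. The database must then show which lesions share a patient code.

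The cost is a sentence or two in the plan and slightly less familiar software output. No extra data are needed, and the results are practically unchanged when events are plentiful.
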